- [19] Failure to respond to 3 or more adequately dosed migraine preventive treatments from different classes (that is, maximum tolerated dose for at least 2 months). Failure to respond due to tolerability issues is not considered a treatment failure. Migraine preventive treatments are defined as Level A and Level B in Table 1 of the American Academy of Neurology's Evidence-based Guidelines Update: Pharmacologic Treatment for Episodic Migraine Prevention in Adults (Silberstein et al. 2012) as well as botulinum toxin A or B.

Diagnostics Assessments

- [20] History of persistent daily headache, cluster headache or migraine subtypes including hemiplegic (sporadic or familial) migraine, ophthalmoplegic migraine, and migraine with brainstem aura (basilar-type migraine) defined by IHS ICHD-3 beta.
- [21] History of headache other than migraine, tension type headache, or medication overuse headache, as defined by IHS ICHD-3 beta within 3 months prior to randomization.
- [22] History of head or neck injury within 6 months prior to Visit 1.
- [23] Patients with a history of traumatic head injury associated with significant change in the quality or frequency of their headaches should be excluded.

Medical Conditions

- [24] Have ECGs showing abnormalities compatible with acute cardiovascular events and/or serious cardiovascular risk, including but not limited to a corrected QT (QTcB [Bazett's]) interval >470 msec for women and >450 for men, or have had myocardial infarction, unstable angina, percutaneous coronary intervention, coronary artery bypass graft, or deep vein thrombosis/pulmonary embolism within 6 months of screening, or have planned cardiovascular surgery or percutaneous coronary angioplasty, or a lifetime history of stroke.
- [25] Patients with a body mass index $\geq 40 \text{ kg/m}^2$.
- [26] Any liver tests outside the normal range at Visit 1 that are clinically significant. Alanine aminotransferase (ALT) >2X upper limit of normal (ULN), or total bilirubin level (TBL) >1.5X ULN, or alkaline phosphatase (ALP) >2X ULN must be discussed and judged not clinically significant by Eli Lilly and Company (Lilly) Medical prior to enrollment.

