Study Period / Analysis	Patient Population	Baseline Observation	Postbaseline Observation(s)
Study Period III	•	.	
Continuous safety analyses (Repeated Measures)	Safety Population with a baseline and at least 1 postbaseline observation	Last of Visits 1–3	All scheduled visits 3 < Visits ≤7
Continuous safety analyses – change from baseline to LOCF endpoint (ANCOVA)	Safety Population with a baseline and at least 1 postbaseline observation	Last of Visits 1–3	Last of Visits 3.01–7
Study Period IV			
TEAEs	Open Label treatment Population	All Visits 1-7	All Visits 7.01–16
Serious Adverse Events, Discontinuations due to Adverse Events	Open Label treatment Population	NA	All Visits 7.01–16
Treatment-emergent abnormal laboratory values	Open Label treatment Population and Patients with normal laboratory values at all nonmissing baseline visits (with respect to direction being analyzed) and who have at least 1 postbaseline observation	Low: Minimum from Visits 1–7 High: Maximum from Visits 1–7 Abnormal: All Visits 1–7	Low: Minimum from Visits 7.01-16 High: Maximum from Visits 7.01-16 Abnormal: All Visits 7.01-16
C-SSRS categorical analyses	Open Label treatment Population and Patients with a baseline and at least 1 postbaseline C-SSRS assessment	Recent History: All Visits 1–7 excluding lifetime ^a All Prior History: Visits 1 – 7 including lifetime ^a	All Visits 7.01–16
Treatment-emergent immunogenicity	Open Label treatment Population	Visit 3	All Visits 7.01–16
Treatment-emergent changes in temperature and weight	Open Label treatment Population and Patients with a baseline and at least 1 postbaseline observation	Low: Minimum from Visits 1–7 High: Maximum from Visits 1–7	Low: Minimum from Visits 7.01–16 High: Maximum from Visits 7.01–16
Treatment-emergent changes in blood pressures, pulse, and ECGs	Open Label treatment Population and Patients with a baseline and at least 1 postbaseline observation	Low: last non-missing from Visits 1–7 High: last non-missing value from Visits 1–7	Low: Minimum from Visits 7.01–16 High: Maximum from Visits 7.01–16

Patient Population with Baseline and Post-baseline Definitions by Study Period and Type of Analysis

			Postbaseline
Study Period / Analysis	Patient Population	Baseline Observation	Observation(s)
Study Period V			
TEAEs	Post-treatment Population	All Visits 1- 16	All Visits 16.01–18
Serious Adverse Events, Discontinuations due to Adverse Events	Post-treatment Population	NA	All Visits 16.01–18

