The baseline and postbaseline values for temperature and weight are defined below (Table CGAI.5.4):

- For continuous analyses of temperature and weight, last nonmissing baseline during the baseline period will be used as the baseline.
- For the analyses of categorical changes of interest in temperature and weight,
 - o the baseline is defined as the minimum value during baseline period when the direction is low.
 - o the baseline is defined as the maximum value during the baseline period when the direction is high.

Table CGAI.5.6. Criteria for Categorical Changes of Interest in Vital Signs and Weight

Parameter	Direction	Criteria	Patients Population defined by Baseline Categories
Systolic BP (mm Hg)	Low	≤90 and decrease ≥20	All patients; >90; ≤90
(sitting)	High	≥140 and increase ≥20	All patients; <140, ≥140
	PCS High	≥180 and increase ≥20	All Patients; <180; ≥180
	Sustained Elevation	≥140 and increase ≥20 at 2 consecutive visits	All patients; < 140; ≥140
Diastolic BP (mm Hg)	Low	≤50 and decrease ≥10	All patients; >50; ≤50
(sitting)	High	≥90 and increase ≥10	All patients; <90; ≥90
	PCS High	≥105 and increase ≥15	All Patients; <105; ≥105
	Sustained Elevation	≥90 and increase ≥10 at 2 consecutive visits	All patients; < 90; ≥90
Diastolic BP (mm Hg) Elevation for 2 consecutive visit (sitting) meeting criteria for diagrams.		Meeting criteria for systolic BP for 2 consecutive visits or meeting criteria for diastolic BP for 2 consecutive visits or both	All Patients
Pulse (bpm) (sitting)	Low	<50 and decrease ≥15	All patients; ≥50; <50
	High	>100 and increase ≥15	All patients; ≤100; >100
	Sustained Elevation	>100 and increase ≥15 at 2 consecutive visits	All patients; ≤100; >100
Weight (kg)	Low	(Loss) decrease ≥7%	All patients
	High	(Gain) increase ≥7%	All patients
Temperature (° F)	Low	<96° F and decrease ≥2° F	≥96°F
	High	≥101° F and increase ≥2° F	<101°F

Abbreviations: BP = blood pressure; bpm = beats per minute; F = degrees Fahrenheit; kg = kilograms; mm Hg = millimeters of mercury; PCS= Potentially Clinically Significant.

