5.5.12.1.4. Electrocardiogram Intervals and Heart Rate

Analyses of corrected QT (QTc) interval will be calculated using 2 correction formulas. The QTcF (msec) will be calculated with Fridericia's formula as QT/RR $^{1/3}$. The Large Clinical Trial Population Based QT Correction (QTcLCTPB) (msec) will be calculated with the formula as QT/RR $^{0.413}$. For the QTc calculations, the unit for QT is milliseconds and the unit for RR is seconds. For patients with QRS \geq 120 msecs at any time during the study, the QT and QTc interval will be excluded from the analyses. A listing of ECG data for patients with QRS \geq 120 msecs at any time during the study will be provided.

The baseline for ECG is defined as the last non-missing baseline value during the baseline period (See Table CGAI.5.4). To be exact,

• For analyses including double-blind treatment phase, the baseline for ECG is defined as the last non-missing value before randomization.

The rationale for using the last available value in the baseline period is to minimize the potential confound of discontinuing or dose stabilization of medications that modulate ECG during the screening phase (which is early in the baseline period).

 Similarly, for other study phases, the baseline is defined as the last non-missing value before patients enter the study phases of interest.
 This baseline definition was chosen to be consistent with the analysis approach for the double-blind treatment phase as described above.

This baseline definition for ECG applies to all analyses (both continuous and categorical, quantitative and qualitative) for ECG.

The baseline and postbaseline values are summarized in Table CGAI.5.4.

The number and percent of patients meeting criteria for treatment-emergent abnormalities in ECG intervals (PR, QRS, QTcF, and QTcLCTPB) and heart rate at any time during study will be summarized. Treatment group comparisons will be performed using CMH test.

Table CGAI.5.7 displays the criteria for treatment-emergent changes in ECG intervals, heart rate, and QTcLCTPB. The absolute threshold in the criteria is based on 1) minimum postbaseline when the direction is low; 2) maximum postbaseline when the direction is high.

For QTcLCTPB, the treatment-emergent low and high criteria are listed by gender and age range, based on Lilly reference ranges.

- For treatment-emergent low analyses: Patients with all normal or high values at baseline (no low values) will be included.

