- For treatment-emergent high analyses: Patients with all normal or low values at baseline (no high values) will be included.
- For treatment-emergent increase analyses: Patients with a baseline and at least 1 postbaseline result will be included.

Table CGAI.5.7. Criteria for Treatment-Emergent Changes in ECG Intervals and Heart Rate

Parameter	Direction	Crite	eria	
Heart Rate (bpm)	Low	<50 and dec	crease ≥15	
	High	>100 and increase ≥15		
PR Interval (msec)	Low	<120		
	High	≥22	20	
QRS Interval (msec)	Low	<6	0	
	High	≥12	20	
QTcF (msec)	Low	Males: <330	Females: <340	
	High	Males: >450	Females: >470	
		>500 r	nsec	
	Increase	Increase >	30 msec	
		Increase >	60 msec	
		Increase >	75 msec	
QTcLCTPB (msec)	Low	Male (All ages): <330;	Female (All ages): <340	
	High	Male	Female	
		Age (yrs): criteria	Age (yrs): criteria	
		<18: >444	<18: >445	
		18-25: >449	18-25: >455	
		26-35: >438	26-35: >455	
		36-45: >446	36-45: >459	
		46-55: >452	46-55: >464	
		56-65: >448	56-65: >469	
		>65: >460	>65: >465	
		>500 msec		
	Increase	ncrease Increase >30 msec		
		Increase >60 msec		
		Increase >	75 msec	

Abbreviations: bpm = beats per minute; msec = milliseconds.

In addition, a descriptive summary of qualitative ECG abnormalities will be conducted which will include summaries of 11 ECG categories (Axis, Rhythm, Conduction, Ischemia, Infarction, Injury, Morphology, U-waves, T-waves, ST Segment, and Other Abnormalities) of qualitative findings at any time postbaseline. A category is a collection of possible descriptions (findings) of 1 qualitative aspect of an ECG. A category name is the name of the qualitative aspect of the ECG (for example, Rhythm, Conduction, Morphology, Ischemia, and so forth). A finding is 1 of the possible specific descriptions (for example, Sinus Bradycardia, Acute Septal Infarction) within a category.

The summaries of the 11 ECG categories will exclude ECGs with any of the following: overall ECG could not be evaluated by the cardiologist, lead reversals or <9 leads, nonmatching demographic data, and those suggesting patient identification errors.

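### The >500 msec QTc rows take the population rule for the sex and age limits, so a patient already above that limit at baseline is not counted when QTc later passes 500 msec

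*SAP*

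**What the plan says.** SAP section 5.5.12.1.4 gives three inclusion rules for categorical ECG changes: low, high and increase. The high rule reads "For treatment-emergent high analyses: Patients with all normal or low values at baseline (no high values) will be included". The increase rule is wider: "For treatment-emergent increase analyses: Patients with a baseline and at least 1 postbaseline result will be included".

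In Table CGAI.5.7 the >500 msec criterion stands under direction High for QTcF and again for QTcLCTPB, ahead of the increase rows. It has no population of its own. The other High criteria are >450 (men) and >470 (women) for QTcF. For the second correction the SAP says "For QTcLCTPB, the treatment-emergent low and high criteria are listed by gender and age range, based on Lilly reference ranges"; between ages 18 and 65 these limits run from 438 to 452 msec in men and from 455 to 469 msec in women.

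For the double-blind phase, "the baseline for ECG is defined as the last non-missing value before randomization". For Study Period IV, Table CGAI.5.4 gives "High: last non-missing value from Visits 1–7"; for Study Period V it uses the last value from Visits 1 to 16. The ECG rows of that table ask only for a baseline and a postbaseline observation.

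Protocol section 5.2, criterion 24, excludes patients with a "corrected QT (QTcB [Bazett's]) interval >470 msec for women and >450 for men".

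**The concern.** A normal-at-baseline filter suits a treatment-emergent shift across a reference limit: a patient already above the limit cannot newly cross it. It does not suit a fixed threshold set well above that limit. Someone at 460 msec can still newly pass 500, and is closer to doing so than someone at 420. Under the high rule that patient is in neither the numerator nor the denominator.

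The SAP handles comparable severe thresholds differently. Table CGAI.5.6 reports potentially clinically significant high systolic pressure for "All Patients; <180; ≥180", that is, for everyone and split at the row's own cut-off. SAP section 5.5.12.1.5 counts ALT/AST, ALP and bilirubin multiples among all patients with a value after baseline, then by baseline subset. Only the severe QTc row takes its population from a lower limit.

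The >500 msec row is the highest absolute QTc threshold in the table, and the expected counts are very small. One omitted case could turn a one into a zero. Two programmers, one following section 5.5.12.1.4 and one following Table CGAI.5.4, could also report different denominators.

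**Working it through.** The plan states no figure to reproduce. The check is whether the omitted group can exist, how wide it is, and how many cases it might cost.

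**1. Can an eligible patient be high at baseline?** Eligibility uses Bazett; the analysis uses QTcF = QT/RR^(1/3) and QTcLCTPB = QT/RR^0.413. Hence QTcF = QTcB × RR^(1/6) and QTcLCTPB = QTcB × RR^0.087.

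- Heart rate 60 (RR = 1): all three are equal, so QTcF cannot exceed 450/470.
- Heart rate 50 (RR = 1.2), QTcB at the cap: QTcF = 450 × 1.0309 = 463.9 (men) and 470 × 1.0309 = 484.5 (women); QTcLCTPB = 450 × 1.0160 = 457.2 and 470 × 1.0160 = 477.5. All four exceed the High limits.
- Heart rate 80 (RR = 0.75): QTcF is at most 428.9/448.0 and QTcLCTPB at most 438.9/458.4.

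Example: a man with QT 490 at heart rate 50 has QTcB 447.3 (eligible), QTcF 461.1 and QTcLCTPB 454.5. Both are high for a man of any age from 18 to 65. A woman with the same values is kept, since her limits are 470 and at least 455.

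**2. Width of the omitted band.** For QTcLCTPB at heart rate 60, band = cap − High limit (zero if negative). The last column is 500 − limit: a kept patient starting at the limit must rise by more than this to pass 500.

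| Group | High limit | Cap | Band | 500 − limit |
|---|---|---|---|---|
| Men 18–25 | 449 | 450 | 1 | 51 |
| Men 26–35 | 438 | 450 | 12 | 62 |
| Men 36–45 | 446 | 450 | 4 | 54 |
| Men 46–55 | 452 | 450 | 0 | 48 |
| Men 56–65 | 448 | 450 | 2 | 52 |
| Women 18–35 | 455 | 470 | 15 | 45 |
| Women 36–45 | 459 | 470 | 11 | 41 |
| Women 46–55 | 464 | 470 | 6 | 36 |
| Women 56–65 | 469 | 470 | 1 | 31 |

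For QTcF a band exists only below heart rate 60.

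**3. Expected loss, double-blind phase (illustration).** The documents give no QTc mean, SD or drug effect, so these are assumptions: women 18–35, mean 415, between-patient SD 16, within-patient SD 9, baseline truncated at 470. Baseline SD = √(16² + 9²) = 18.4; correlation = 256/337 = 0.76; conditional SD = 18.4 × √(1 − 0.76²) = 11.9. For baseline b and mean shift d,

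P(post > 500) = 1 − Φ((500 − [415 + 0.76(b − 415) + d]) / 11.9).

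Integrating over b from 455 to 470 (1.3% of patients) gives 0.064, 0.84 and 6.1 lost crossings per 10,000 for d = 10, 20 and 30 msec. If all 570 active patients (285 + 285, SAP section 5.2) were in this stratum, that is 0.004, 0.05 and 0.35 patients.

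Harsher settings: with mean 420, total SD 25, correlation 0.5 to 0.8 and all 570 patients women aged 26–35, the loss is at most 0.11 with no shift and 1.2 to 1.4 with a 20 msec mean shift. That corner puts everyone in the widest-band stratum.

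**4. Study Periods IV and V.** Under the Schedule of Activities the ECG before Period IV is at Visit 7 and the one before Period V is at Visit 16. Criterion 24 does not limit either. A patient at 490 msec at Visit 7 needs a rise of more than 10 msec to pass 500, yet is omitted from the Period IV count, while a patient at the limit who needs more than 31 to 62 msec is kept.

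**The case against.** The strongest reply is that the SAP does not clearly apply the filter. The ECG rows of Table CGAI.5.4 have no normal-at-baseline condition, whereas the laboratory rows do, and under those ECG rows the patient at 505 msec is counted. High at baseline is also never defined for the >500 row; a programmer might read it as not already above 500. The first part stands: the documents conflict. The second fits poorly, because the bullet asks for normal or low values and 490 msec is neither. Section 5.5.12.1.4 is also the more specific text.

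Second, a case would not vanish from the report. The >30, >60 and >75 msec increase rows and the continuous analyses keep these patients, and ECG findings that lead to a diagnosis are reported as adverse events. A combined Period III/IV categorical analysis is also planned with the pre-randomization baseline, so a patient normal at Visit 3 and at 490 at Visit 7 can be counted there. This stands and limits the harm. It does not close the gap: none of the increase rows or mean changes shows an absolute crossing, and no combined categorical analysis covers Period V.

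Third, a reader might infer that the rule removes most >500 crossings. In the model above the omitted women aged 18–35 supply about 85%, 74% and 58% of crossings at shifts of 10, 20 and 30 msec. The documents do not support that as a finding. The shares rest on assumed SDs and shifts, on the widest-band stratum, and on a Bazett cap applied as if heart rate were 60. In women 46–55 they fall to 34% and 22% at shifts of 20 and 30; in women 56–65 to 6% and 3%; in men 46–55 to zero.

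**Conclusion.** The point holds as a defect of specification. The rule in section 5.5.12.1.4 omits from the >500 msec count anyone above the sex limit (QTcF) or the sex-and-age limit (QTcLCTPB) but at or below 500 at baseline. It conflicts with the ECG rows of Table CGAI.5.4 and differs from the SAP's own treatment of blood pressure and liver thresholds.

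In the double-blind phase the effect is small: an omitted QTcF band only below heart rate 60, a QTcLCTPB band of at most 12 msec (men) or 15 msec (women) at heart rate 60, and an expected loss well below one patient under the main assumptions. This takes criterion 24 as holding at the baseline ECG. Periods IV and V are more exposed, because baseline can be an on-treatment value with no eligibility cap; no size can be given from the documents.

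It should not be read as evidence that a QT effect exists or would be hidden. The plan states no QT effect, and the affected patients remain in other outputs. This is a cheap improvement that makes one safety count mean what its label says.

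**What to change.** Add one sentence to the inclusion bullets in SAP section 5.5.12.1.4: *for the >500 msec criterion (QTcF and QTcLCTPB), every patient whose baseline value is at most 500 msec and who has one or more postbaseline values is included.* State that the normal-or-low filter applies only to the sex- and age-specific limits. Optionally, also show the >500 count split by baseline normal versus high, as Table CGAI.5.6 does for blood pressure.

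Align the ECG rows of Table CGAI.5.4 for Study Periods III, IV and V with the bullets, so that one population is stated for each criterion.

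Cost: one SAP sentence, a table alignment and one changed denominator. No new data are needed. The count may become slightly less favourable.

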5.5.12.1.5. Laboratory Tests

The incidence rates of patients with treatment-emergent abnormal high or low laboratory values based on Covance reference ranges at any time postbaseline will be assessed using CMH test for each laboratory test.

Patients will be defined as having a treatment-emergent low value if they have all normal or high values at baseline, followed by a value below the lower reference limit at any postbaseline visit. Patients with all normal or high values at baseline (no low values) will be included in the analysis of treatment-emergent low laboratory values. Patients will be defined as having a treatment-emergent high value if they have all normal or low values at baseline, followed by a value above the upper reference limit at any postbaseline visit. Patients with all normal or low values at baseline (no high values) will be included in the analysis of treatment-emergent high laboratory values.

For analytes simply classified as normal or abnormal, patients will be defined as having a treatment-emergent abnormal value if they have all normal values at baseline, followed by an abnormal value at any postbaseline visit. Patients with all normal values at baseline will be included in the analysis of treatment-emergent abnormal laboratory values.

The incidence of patients with the following elevations in hepatic laboratory tests at any time postbaseline will also be summarized and compared between treatment groups using CMH test.

- The percentages of patients with an alanine aminotransferase (ALT) or aspartate aminotransferase (AST) measurement greater than or equal to 3 times (3×), 5 times (5×), and 10 times (10×) the Covance upper limit of normal (ULN) during the treatment period will be summarized for all patients with a postbaseline value.
- The percentages of patients with an Alkaline phosphatase (ALP) greater than or equal to 2 times (2×) the Covance ULN during the treatment period will be summarized for all patients with a postbaseline value.
- The percentages of patients with a total bilirubin (TBIL) measurement greater than or equal to 2 times (2×) ULN during the treatment period will be summarized for all patients with a postbaseline value.

Hy's law is defined as the combination of drug related elevation of ALT \geq 3× ULN and TBIL \geq 2× ULN, in the absence of significant cholestasis (that is ALP< 2× ULN), and in the absence of other causes of liver injury.

The analysis of elevation in ALT, AST, ALP, and TBIL will contain 3 subsets:

 patients whose nonmissing maximum baseline value is less than or equal to 1× ULN for ALT, AST, ALP, and TBIL.

- patients whose nonmissing maximum baseline value is greater than 1× ULN for ALT, AST, ALP, and TBIL, at the same time less than or equal to 2× ULN for ALT and AST, 1.5× ULN for ALP and TBIL.
- patients whose nonmissing maximum baseline value is greater than 2× ULN for ALT and AST, 1.5× ULN for ALP and TBIL.

5.5.12.1.6. *Immunogenicity*

To evaluate the changes in immunogenicity data (Anti-LY2951742 [ADA and NAb]) after treatment, the following statistical analyses are planned for comparison between treatment groups:

- The incidence of ADA positive during baseline will be summarized.
- The incidence of treatment-emergent ADA (TE ADA) between treatment groups will be summarized and compared for SP III. The incidence of TE ADA for LY-treated patients during LY treatment and the incidence of TE ADA for LY-treated patients during LY treatment and post-treatment phase combined will be summarized. This analysis will be done for each immunogenicity analyte (ADA and NAb). The baseline and postbaseline definitions for each Study Period is shown in Table CGAI.5.4. Treatment-emergent ADA will be defined as any of the following:
 - o a negative baseline result and a positive postbaseline ADA result with a titer ≥20. This is also called treatment-induced ADA.
 - a positive baseline result and a positive postbaseline ADA result with a ≥4-fold increase in titers (for example, baseline titer of 10 increasing to ≥40 postbaseline). This is called treatment-boosted ADA.
- The incidence of TE ADA and NAb Positive combined between treatment groups will be summarized for the same time periods as planned for the incidence of TE ADA.

The following will also be provided:

- Listing of subjects with TE ADA at any time during study, NAb Status will also be displayed.
- Listing of subjects with ADA detected at any time during study, excluding subjects with TE ADA.
- Line plot of ADA titers over time for each subject with TE ADA at any time.
- Listing of subjects with TE hypersensitivity reactions or TEAEs related to injection sites for subjects with ADA present at any time.

In addition, as summarized in the immunogenicity addendum to Study CGAI protocol (Addendum 7), additional data will be collected after patients completed or discontinued from study, to characterize the time course of treatment-emergent anti-drug antibodies (ADA).

Individual patient listing of those data will be created, including concomitant medication, adverse events and ADA measurements.

